$[^{18}\text{F}]\text{GTP1}$ and amyloid radioligands will be used for tau PET and amyloid PET imaging, respectively. For each PET imaging procedure, a single dose of the relevant radioligand will be injected prior to the PET scan. Details for radioligand doses and administration are provided in the Technical Operations Manuals for the various radioligands.

Statistical Methods

Primary Analysis

The efficacy analyses will be based on the modified intent-to-treat population, which is defined as all randomized patients who receive at least one dose of study drug and have at least one postbaseline primary efficacy Clinical Dementia Rating–Sum of Boxes (CDR-SB) measurement. For the efficacy analysis, patients will be grouped according to the treatment assigned at randomization. The primary efficacy endpoint is change in CDR-SB score from baseline to Week 73. The difference in mean change from baseline to Week 73 between MTAU9937A- and placebo-treated patients will be estimated using an analysis of covariance model adjusting for *ApoE4* status and baseline *clinical* status (i.e., prodromal AD vs. mild AD dementia). Confidence intervals as well as least squares estimates will be used to aid in interpretation of study results.

The safety analysis will be based on all randomized patients who receive at least one dose of either MTAU9937A or placebo, or GTP1. Patients will be grouped according to MTAU9937A treatment actually received. All adverse events that occur after informed consent is given will

be summarized by mapped term, appropriate thesaurus level, and toxicity grade. In addition, all serious adverse events, including deaths and events leading to discontinuation, will be listed separately and summarized. Laboratory data will be summarized by descriptive statistics by treatment group. In addition, all laboratory abnormalities will be summarized by grade using the WHO grading scale. Dose-limiting adverse events and adverse events of special interest will be listed and summarized by treatment group. Vital signs (pulse rate, blood pressure, body temperature, and respiratory rate), weight, and other disease-specific data will be summarized by descriptive statistics by treatment group. Changes from baseline will be summarized by treatment group.

- A primary analysis will occur after the last patient has completed the Week 73 assessment.
- A final analysis will occur after the last patient has finished the OLE and completed the Week 169 assessment.

Determination of Sample Size

This study *has enrolled 457* patients, randomized to one of three active IV dose arms or to an IV placebo dose arm in a 2:3:2:3 ratio. *The prior projected sample size of 360 patients* provides reasonable precision for estimating a clinically significant treatment effect on CDR-SB scores when MTAU9937A is compared with placebo. Assuming an observed 0.6-point difference in mean CDR-SB decline between the 4500 mg MTAU9937A arm and placebo at Week 73, a standard deviation across patients of 2, and a 25% dropout rate, a 90% confidence interval on the population treatment effect point estimate for the CDR-SB is approximately 0.08–1.12.

Optional Interim Analysis

To adapt to information that may emerge during the course of this study, the Sponsor may choose to conduct an interim efficacy analysis. The rationale for conducting an interim analysis will be on the basis of factors and information external to this study such as new, emergent data from other clinical trials.

If an interim analysis is conducted, the Sponsor will remain blinded. The interim analysis will be conducted by an external statistical group and reviewed by the iDMC. Interactions between the iDMC and Sponsor will be carried out as specified in the iDMC charter.

The decision to conduct an optional interim analysis, along with the rationale and timing, will be documented in the protocol. Statistical details for the interim analysis will be contained within the Statistical Analysis Plan (SAP). A substantial protocol amendment (in the European Union) or the SAP (other jurisdictions) will be submitted to relevant health authorities, as appropriate, prior to the conduct of the interim analysis. The iDMC charter will also be updated to document potential recommendations the iDMC can make to the Sponsor as a result of this analysis and the iDMC charter will be submitted to relevant Health Authorities. All documents submitted to health authorities would be simultaneously submitted to the study master file to further document this information appropriately. The Clinical Study Report will also document that such an interim analysis occurred.

If the interim analysis plan allows for early assessment of efficacy, the type I error rate will be controlled to ensure statistical validity is maintained. Specifically, the Lan-DeMets α -spending function that approximates the O'Brien-Fleming boundary will be applied to determine the critical value for stopping for positive efficacy at the interim analysis. Additional criteria for recommending that the study be stopped for positive efficacy may be added to the iDMC charter. If the study continues beyond the interim analysis, the critical value at the final analysis would be adjusted accordingly to maintain the overall type I error rate, per standard Lan-DeMets methodology. The select efficacy endpoints provided to the iDMC as part of ongoing safety review do not enable and are not considered sufficient for a formal interim analysis to assess early efficacy or futility.

If the interim analysis plan allows for early assessment of futility, the threshold for declaring futility will include an assessment of the predictive probability that the primary endpoint will achieve statistical significance. An interim analysis that might lead to stopping the study for futility will not occur before at least 50% of the information has been accumulated for the primary endpoint.

LIST OF ABBREVIATIONS AND DEFINITIONS OF TERMS

Abbreviation	Definition
[¹⁸ F]GTP1	fluorine-18 Genentech tau probe 1
A β	β -amyloid
AD	Alzheimer's disease
ADA	anti-drug antibody, also known as anti-therapeutic antibody (ATA)
ADAS-Cog	Alzheimer's Disease Assessment Scale–Cognitive Subscale
ADCS-ADL	Alzheimer's Disease Cooperative Study Group–Activities of Daily Living Inventory
ADL	activities of daily living
AUC	area under the concentration–time curve
CaGI-Alz	Caregiver Global Impression of Change Scales for Alzheimer's disease
CDR	Clinical Dementia Rating
CDR-GS	Clinical Dementia Rating–Global Score
CDR-SB	Clinical Dementia Rating–Sum of Boxes
C _{max}	maximum concentration
COA	clinical outcome assessment
CRO	contract research organization
CSF	cerebrospinal fluid
C-SSRS	Columbia-Suicide Severity Rating Scale
DVF	Diagnostic Verification Form
EC	Ethics Committee
eCRF	electronic Case Report Form
EDC	electronic data capture
F _c	fragment crystallizable
FcRn	neonatal Fc receptor
FDA	Food and Drug Administration
GLP	Good Laboratory Practices
GTP1	Genentech tau probe 1
HBsAg	hepatitis B surface antigen
HCV	hepatitis C virus
HIPAA	Health Insurance Portability and Accountability Act
HV	healthy volunteer
iADL	Instrumental Activity of Daily Living
ICH	International Conference on Harmonisation
iDMC	independent Data Monitoring Committee
IMP	investigational medicinal product
IND	Investigational New Drug (application)

Abbreviation	Definition
IRB	Institutional Review Board
IxRS	interactive voice or web-based response system
LP	lumbar puncture
mAD	mild AD
MCI	mild cognitive impairment
MMSE	Mini-Mental State Examination
MRI	magnetic resonance imaging
NIA-AA	National Institute on Aging/Alzheimer's Association
NIMP	Non-investigational medical product
OLE	open-label extension
pAD	prodromal AD
PD	pharmacodynamic
PET	positron emission tomography
PK	pharmacokinetic
Q2W	every 2 weeks
Q4W	every 4 weeks
QTcF	QT interval corrected using Fridericia's formula
RBANS	Repeatable Battery for the Assessment of Neuropsychological Status
RBR	Research Biosample Repository
RUD	Resource Utilization in Dementia
SAP	Statistical Analysis Plan
SNP	single nucleotide polymorphism
T4	thyroxine
TK	toxicokinetic
TSH	thyroid-stimulating hormone
ULN	upper limit of normal
URTI	upper respiratory tract infection
WES	whole exome sequencing
WGS	whole genome sequencing
YTE	heavy chain with M249Y, S251T, and T253E mutations

1. **BACKGROUND**

1.1 **BACKGROUND ON ALZHEIMER'S DISEASE**

Alzheimer's disease (AD) is the most common cause of dementia, affecting an estimated 4.5 million individuals in the United States and 26.6 million worldwide (Hebert et al. 2003; Brookmeyer et al. 2007). The disease is characterized pathologically by the accumulation in the brain neocortex of extracellular β -amyloid ($A\beta$) peptide-containing plaques and intracellular neurofibrillary tangles containing aggregates of the microtubule associated protein tau. Diagnosis is made through the clinical assessment of the neurologic and neuropsychiatric signs and symptoms of AD and the exclusion of other causes of cognitive dysfunction. AD is commonly classified into preclinical, prodromal, mild, moderate, and severe stages by the presence and severity of clinically relevant functional and/or cognitive decline, and categorization is often facilitated by global measures, such as the Clinical Dementia Rating scale (CDR; Morris 1993) or the Mini-Mental State Examination (MMSE; Folstein et al. 1975). Approved medical therapies that inhibit acetylcholinesterase activity or antagonize *N*-methyl-d-aspartate receptors in the brain may temporarily improve the symptoms of AD in some patients but do not modify the progression of the disease (Cummings 2004).

The deposition of extracellular amyloid plaques and intracellular tau aggregates in the brain are the hallmark pathologic findings in AD, first reported by Alois Alzheimer in 1906. Intracellular neurofibrillary tangles are composed of aggregated and abnormally phosphorylated tau protein. Tau, encoded by the *MAPT* gene, is expressed in the human brain as six splice isoforms, with lengths of 352–441 amino acids. The six isoforms comprise combinations of three variant near-amino-terminal repeat domains (0N, 1N, and 2N) and two variant carboxy-terminal repeat domains (3R and 4R) (Wang and Mandelkow 2016). While the intracellular aggregates are found as neurofibrillary tangles in the neuron soma and as neuropil threads in the dendritic compartment, it is believed that the spread of tau pathology through the brain is mediated by soluble tau in the extracellular brain environment (Braak and Tredici 2015; Wang and Mandelkow 2016).

The spatial distribution of tau pathology in AD patients correlates with decline in the cognitive domains subserved by the affected cortical networks (Ossenkoppele et al. 2016). Knockout of the tau gene in an AD transgenic mouse model is protective against cognitive deficits (Roberson et al. 2007). Therapies that reduce the spread of tau in the brain may alleviate cognitive dysfunction and block further synaptic loss, axon degeneration, and neuronal cell death.

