For sites where [^{18}F]GTP1 PET imaging is not available, or where local restrictions preclude [^{18}F]GTP1 PET imaging, patients must have CSF collected via lumbar puncture (LP) at baseline, Week 49, and Week 73 during the double-blind treatment period; those patients continuing into the optional OLE period are encouraged to have an LP performed at Week 169. If an LP was performed during screening for the assessment of amyloid positivity, CSF from this LP will be used for the baseline measurement; otherwise, an LP must be performed during the baseline visit (after randomization).

[^{18}F]GTP1 PET, amyloid PET, and MRI evaluation will use a standard protocol, provided in the imaging technical operations manuals. Screening amyloid PET and MRIs will be read by a central reader to determine eligibility. Screening amyloid CSF analysis will be performed by a central laboratory.

PET scans should be performed only if the investigator has determined that the total past and planned annual radiation exposure does not exceed local guidelines. Radiation exposure for [^{18}F]GTP1 doses can be found in the [^{18}F]GTP1 Investigator's Brochure. Radiation exposure for doses of the amyloid radioligands can be found in the local labeling instructions or, depending on locality, in the Investigator's Brochures.

Number of Patients

This study *has enrolled 457 patients and is being* conducted at 97 sites in North America, Europe, and the Asia-Pacific region.

Target Population

Inclusion Criteria

Patients must meet the following criteria for study entry:

- Signed Informed Consent Form by the patient (co-signed by the patient's legally authorized representative, if required by the local regulations, guidelines, and independent ethics committee or institutional review board)

Patients should be judged by the investigator to be lucid and oriented when giving the informed consent.

- Age between 50 and 80 years, inclusive, at time of signing Informed Consent Form
- NIA-AA core clinical criteria for probable AD dementia or pAD (consistent with the NIA-AA diagnostic criteria and guidelines for MCI)
- Evidence of the AD pathological process, by a positive amyloid assessment either on CSF A β_{1-42} as measured on Elecsys β -Amyloid(1–42) Test System OR amyloid PET scan by visual read by the core/central PET vendor as specified in the Imaging Review Charter.

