4.2 METHOD OF TREATMENT ASSIGNMENT AND BLINDING

Patients will be randomly assigned to one of three active, IV dose arms (1500, 4500, or 8100 mg MTAU9937A) or to an IV placebo dose arm in a 2:3:2:3 (1500mg:4500 mg: 8100 mg:placebo) ratio. Randomization of patients will be managed by a central interactive voice or Web-based response system (IxRS) vendor using stratified permuted block randomization. The randomization will be stratified by dementia status (pAD vs. mAD) and APOE status (ApoE4+ vs. ApoE4-).

Patients, study site personnel who will evaluate patient status, contract research organization (CRO) personnel who will review CRFs, other Sponsor agents (with the exception of the IxRS vendor), and the Sponsor will remain blinded to treatment assignment. The unblinded site pharmacist and the unblinded CRO monitor will be unblinded to treatment assignment.

The iDMC and independent data coordinating center vendor will be unblinded to treatment assignment.

Although PK samples must be collected from participants assigned to placebo to maintain the blinding of treatment assignment, PK assay results for the placebo participants are generally not needed for the safe conduct or proper interpretation of this trial. Laboratory personnel responsible for performing PK assays will be unblinded to participants' treatment assignments to identify appropriate PK samples to be analyzed. Samples from participants assigned to the placebo arm will not be analyzed except by request (e.g., to evaluate a possible error in dosing).

If unblinding is necessary for immediate patient management (e.g., in the case of a serious adverse event for which patient management might be affected by knowledge of treatment assignment), the investigator will be able to break the treatment code by contacting the IxRS. The investigator is not required to contact the Medical Monitor prior to breaking the treatment code; however, the treatment code should not be broken except in emergency situations. If the investigator wishes to know the identity of the study drug for any reason other than a medical emergency, he or she should contact the Medical Monitor directly. The investigator should document and provide an explanation for any non-emergency unblinding. The investigator will be able to break the treatment code by contacting the IxRS.

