The study consists of a screening period, a double-blind treatment period, an optional OLE period, and a safety follow-up period (see protocol for details). An extended baseline visit (up to 15 days) is included in the double-blind treatment period, following randomization and prior to the initiation of study drug. Study drug (MTAU9937A or placebo) will be administered intravenously in the double-blind treatment period, and MTAU9937A will be administered intravenously in the optional OLE period. Study drug administration will occur every 2 weeks (Q2W) for the first three doses of the double-blind treatment period and every 4 weeks (Q4W) thereafter in the double-blind treatment period. MTAU9937A will be administered Q4W in the OLE period. Study treatment is defined as study drug plus the PET radioligand used during PET imaging procedures (^{18}F]GTP1 for tau PET imaging and the amyloid radioligand for amyloid PET imaging).

This study has enrolled 457 patients at 97 sites in North America, Europe, and the Asia-Pacific region. Patients were randomly assigned to one of three active, IV dose arms (1500 mg, 4500 mg, or 8100 mg MTAU9937A) or to an IV placebo dose arm in a 2:3:2:3 (1500 mg:4500 mg:8100 mg:placebo) ratio. All patients participating in the OLE will receive

MTAU9937A 4500 mg IV. To maintain balance in dementia status and APOE status between treatment arms, randomization will be stratified by dementia status (pAD vs. mAD) and APOE status (ApoE4+ vs. ApoE4-).

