3. STUDY CONDUCT

3.1 RANDOMIZATION ISSUES

Patients will be randomly assigned to one of three active, IV dose arms (1500, 4500, or 8100 mg MTAU9937A) or to an IV placebo dose arm in a 2:3:2:3 (1500mg:4500 mg: 8100 mg:placebo) ratio. Randomization of patients will be managed by a central interactive voice or Web-based response system (IxRS) vendor using stratified permuted block randomization. The randomization will be stratified by dementia status (pAD vs. mAD) and APOE status (ApoE4+ vs. ApoE4-). The iDCC vendor periodically checks the IxRS to ensure that randomization is being performed correctly and that the correct kits are being assigned.

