3.2 INDEPENDENT REVIEW FACILITY

Clinicians/raters (but not caregivers or patients) will use an electronic device to capture clinical outcome assessment (COA) data from all patients and/or caregivers enrolled in this study. This includes the primary and all secondary endpoints. COA data from the electronic device will be transmitted to a centralized database maintained by the electronic device vendor.

The COA scales and assessments for this study will be provided unless otherwise specified. Whenever possible, there should be consistency in the rater and caregiver who complete the scales for each patient throughout the duration of the study. Potential raters should be designated at each site and will receive training and be approved by the rating-scale vendor prior to being allowed to administer any cognitive assessments/ rating scales in the study. Administration of cognitive assessments/rating scales (i.e., the COAs) will be done in accordance with instructions provided in the GN39763 COA Manual and the training/documentation provided by the rating-scale vendor.

In addition, given that the primary outcome measure in this study involves subjective judgment, the adequacy of patient interviews and ratings will be monitored by an endpoint reliability program administered by the rating-scale vendor; this is considered to be an essential part of good research methodology. Prior studies have clearly demonstrated that the failure to

adequately monitor such ratings can substantially increase the risks of failed trials ([Becker and Greig 2008](#); [Kobak 2010](#)).

Please see the GN39763 COA Manual for instructions on COA administration order, specification of list versions to use at each visit, rater roles, restrictions on raters, and additional details on COA administration and the endpoint reliability program.

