4.4 EFFICACY ANALYSIS

All efficacy analyses will be based on the modified intent-to-treat populations defined in Section 4.1.2. The primary and secondary endpoints will be analyzed as change scores, calculated as follows:

Outcome measure change score = (post-baseline value – baseline value)

In the above determination of change score for CDR-SB and RBANS, the baseline value will be defined as the average of all non-missing values before the first dose of study drug, which should be an average of the screening and baseline values. For all other cognitive and biomarker endpoints, baseline value will be defined as latest observed value before the first dose of study drug.

For the primary and secondary endpoints, mean changes from baseline will be compared across treatment arms using mixed-models for repeated measures (MMRM). Each model will have an intercept term, a term for baseline value of the endpoint, a term for APOE4 strata (carrier vs. non-carrier), a term for dementia status strata (pAD vs. mAD), an interaction term of the two stratification factors, categorical visit terms, a term for treatment group, a term for baseline age, and terms for treatment-by-visit interactions. This will be implemented using SAS proc mixed syntax similar to the excerpt below:

```
proc mixed data=data;  
class PATNUM VISIT TRT APOE4 DEMSTATUS;  
model var = BASE BAGE APOE4 DEMSTATUS APOE4*DEMSTATUS VISIT TRT TRT*VISIT  
/solution noint ddfm=kr;  
repeated VISIT / subject=PATNUM type=UN;  
lsmeans VISIT*TRT / pdiff cl alpha=0.05;  
estimate 'MTAU9937A vs Placebo Wk 73' TRT -1 1/cl;
```

An unstructured variance-covariance matrix for within-subject errors will be assumed. If the unstructured covariance structure matrix results in a lack of convergence, the heterogeneous Toeplitz covariance structure followed by the heterogeneous first-order autoregressive

covariance structure will be used. In these cases, the sandwich estimator will be used to get the variance of the treatment effect estimator.

If model assumptions are violated (e.g. large deviations from normality of residuals), alternative modeling strategies including data transformations, permutation-based approaches, and/or robust mixed effects modeling methodology (Koller, Journal of Statistical Software 2016) will be used as appropriate for additional sensitivity analyses.

Comparisons of Interest

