4.4.4 Subgroup Analyses

Exploratory subgroup analyses of the primary efficacy endpoint will be performed to evaluate the consistency of the primary analysis results across pre-specified subgroups defined by demographic and baseline characteristics. The following subgroups will be analyzed with respect to the primary efficacy endpoint:

- Age (≤ 65 years, > 65 years)
- Sex (male, female)
- Dementia status (prodromal, mild)
- APOE4 status (positive, negative)
- Geographic region (North America, EU, rest-of-world)

Biomarker subgroup analyses are specified in Section 4.4.5.

For above subgroup analyses, a MMRM model as specified for the primary analysis in Section 4.4 will be used for each subgroup analyses based on the available data subset for the patient subgroup of interest with the exception of the dementia status and APOE4 status subgroup analyses (bullets 3 and 4) which will not contain the respective indicator variables since they are being used to define the subgroup.

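### Region is left out of the primary MMRM and the per-visit sensitivity models of a three-region, 97-site trial; adding it with a region-by-visit term would be a cheap, small gain in precision, and leaving it out is not a bias or an error

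*Protocol*

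**What the plan says.** The Protocol Synopsis (Number of Patients) describes the study as "conducted at 97 sites in North America, Europe, and the Asia-Pacific region". SAP Section 2 reports that "This study has enrolled 457 patients at 97 sites in North America, Europe, and the Asia-Pacific region", which is about 4.7 patients per site (457/97). Protocol 4.2 has assignment "managed by a central interactive voice or Web-based response system (IxRS) vendor using stratified permuted block randomization". SAP 3.1 names the strata: "The randomization will be stratified by dementia status (pAD vs. mAD) and APOE status". Neither region nor site is among them.

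The MMRM in SAP 4.4 has "a term for APOE4 strata (carrier vs. non-carrier), a term for dementia status strata (pAD vs. mAD"), the interaction of these two factors, the baseline value, baseline age, visit, treatment and treatment-by-visit. The least-squares sensitivity models in SAP 4.4.3 use the same baseline covariates. The ANCOVA in Protocol 6.4.1 adjusts for ApoE4 and baseline clinical status only. Region is in none of these.

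Region appears once as an analysis variable, in the exploratory subgroup list of SAP 4.4.4: "Geographic region (North America, EU, rest-of-world").

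SAP 3.2 introduces the endpoint reliability program with the remark "given that the primary outcome measure in this study involves subjective judgment".

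**The concern.** Region is fixed before randomization and known for every patient. On the documents' own terms it could be related to measured decline. The CDR is a semi-structured interview with patient and caregiver (Protocol 4.5.7.2), instruments are translated where needed (Protocol 4.5.7), and symptomatic AD medication may change during the study according to local judgment (Protocol 4.4.1).

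If regions differ in Week 73 change, two things follow. The between-region part stays in the residual variance. And because nothing in the randomization balances region, the arms can differ in regional mix by chance, which moves the realised difference.

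The first test (pooled 4500 mg and 8100 mg against placebo) gates all later formal testing and has a stated power of only 68%. A small gain in precision is therefore worth having. A region term fixed in advance also answers whether a result reflects regional mix, and that answer carries less weight if the term is added after unblinding.

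**Working it through.** **Inputs from SAP 2.2 and 4.4.** Difference 0.6; SD 2; dropout 25%; 228 pooled active and 137 placebo patients before dropout; two-sided 5%.

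**The plan's own figure.**
- After dropout: 228 × 0.75 = 171 and 137 × 0.75 = 102.75.
- k = √(1/171 + 1/102.75) = 0.1248; SE = 2 × 0.1248 = 0.2496.
- Power = Φ(0.6/0.2496 − 1.96) = 67.1%, against the stated 68%. The inputs are read correctly.

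**Assumptions, because the documents give no regional figures.** Regional shares 50/35/15, 40/40/20 or 60/35/5 per cent. Largest difference d between regional means of Week 73 change: 0.3 to 1.0 point. The middle region lies halfway or at either end.

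**Formulas.**
- Between-region variance: vb = Σ share × (regional mean − overall mean)².
- Share of variance explained: R² = vb/4.
- SD of the chance shift in the contrast without region: √vb × k.
- SE with region fully removed: √(4 − vb) × k.

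**Extremes.**
- Largest vb: two halves at opposite ends (50% against 35% + 15%), vb = d²/4. This is the ceiling for any shares.
- Smallest vb in the grid: the 5% region alone at one end, vb = 0.05 × 0.95 × d² = 0.0475 d².

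| d | vb | R² | chance-shift SD | 95% range | power |
|---|---|---|---|---|---|
| 0.3 | 0.0043–0.0225 | 0.11–0.56% | 0.008–0.019 | up to ±0.04 | 67.2–67.4% |
| 1.0 | 0.0475–0.25 | 1.2–6.3% | 0.027–0.062 | up to ±0.12 | 67.7–69.9% |

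At the extreme, ±0.12 is about 20% of the 0.6-point planning effect.

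**How far the mix can differ by chance.** For a region with share p, the 95% range for the difference in its share between the pooled arm and placebo is ±1.96 × √(p(1−p)) × k. That is about ±7 percentage points at p = 0.10 and ±12 at p = 0.50.

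**Validity without region.** In a simulation under no treatment effect (20,000 runs each, regional differences of 0.5 and 1.0 point), the unadjusted test rejected in 5.3% and 5.2% of runs (Monte Carlo SE about 0.15 points). That is about nominal.

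**Which region term is needed.** A main effect alone fits one constant regional gap across Weeks 25, 49 and 73. Suppose the gap grows linearly, x = (1/3, 2/3, 1) of its Week 73 size. Under generalised least squares the constant is 1′V⁻¹x / 1′V⁻¹1.
- Equal visit SDs and a common correlation: 0.67.
- SDs 1.2, 1.6, 2 and common correlation 0.4: 0.46.
- SDs 1.0, 1.5, 2 and common correlation 0.8: 0.11.

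So if SDs rise over time, a main effect captures only about 11% to 46% of the Week 73 gap. The power figures in the table need region-by-visit.

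**The case against.** Leaving out a covariate that was not a stratification factor contradicts nothing in either document. The SAP adjusts for both strata, their interaction, the baseline value and age. The chance shift is ordinary sampling error that the standard error already covers: at most about 6% of the contrast's variance. All of this stands.

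A reader might infer that the CDR-SB contrast is biased by regional mix, or that regional rating habits contaminate it. The documents do not support either. Randomization keeps the contrast unbiased on average. A constant regional leniency or translation effect cancels in the change from the patient's own baseline, and the plan has rater training, vendor approval and the endpoint reliability program. Only regional differences in measured decline remain.

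Every regional input above is assumed. SD 2 is a planning SD across patients, and baseline value, age and strata may already absorb part of any regional difference. The power figures are therefore upper values.

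The objection does not remove the point. The reliability program limits rating variation but does not adjust for differences in population or care. The subgroup analysis examines consistency and leaves the primary contrast as it is. The plan already includes age, which is not a stratum, so it is not restricted to stratification factors.

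**Conclusion.** The point holds as an inexpensive improvement in precision. The first test would gain between about 0.1 and 2.8 percentage points of power (67.1% to 67.2% at the low end, to 69.9% at the high end). This assumes largest regional differences of 0.3 to 1.0 point, full removal of the regional difference at Week 73, and no overlap with existing covariates. If regions hardly differ, the gain is negligible.

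The region variable is also less ready than it looks. SAP 4.4.4 uses EU and rest-of-world, while the protocol and SAP Section 2 speak of Europe and Asia-Pacific. European sites outside the EU have no stated category.

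**What to change.** Before the Sponsor is unblinded for the analysis (SAP 2.3):

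1. Define the assignment of countries to regions, reconciling the SAP 4.4.4 labels with those in the protocol and SAP Section 2.
2. Add REGION and REGION*VISIT to the CLASS and MODEL statements of the SAP 4.4 MMRM, for the primary and secondary endpoints.
3. Add REGION to the per-visit least-squares models in SAP 4.4.3.
4. Omit it in the region subgroup models, as SAP 4.4.4 already does for dementia and APOE4 status in theirs.

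If the primary model is to stay as it is, pre-specify the region-adjusted MMRM as a sensitivity analysis.

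Cost: 2 degrees of freedom for region plus 2 × (3 − 1) = 4 for region-by-visit, 6 in all over three post-baseline visits, and 2 in each least-squares model. No new data are needed. The rest-of-world cell may be small: at an assumed 5% share, 0.05 × 457 ≈ 23 patients over four arms. Stratifying by region is no longer possible because enrolment is complete, and site as a fixed effect is impractical at about 4.7 patients per site.
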